2.7 Statistical Analysis and Sample Size Justification

The PI, [name], will be responsible for analyzing all study data. The blind will be held at the local site by the VAPAHCS research pharmacist. Once all data has been cleaned and locked, [name] will be unblinded to conduct the final analyses.

Variables/Time Points of Interest

Objective and subjective sleep variables (total sleep time, sleep efficiency, wake after sleep onset, sleep quality) will be collected continuously during the 2-week baseline and the three-week intervention. Subjective alertness assessment will also be collected continuously over the five-week protocol. All of these will be used in the study analyses.

Statistical Methods

The purpose of this study is to test the hypothesis that ingestion of 10 mg of suvorexant 30 minutes prior to daytime sleep initiation in individuals working overnight shifts will significantly improve both objective (total sleep time, sleep efficiency, wake after sleep onset) and subjective (sleep quality) measures of sleep. A secondary goal is to test the hypothesis that ingestion of 10 mg of suvorexant 30 minutes prior to daytime sleep initiation will (1) increase subjective measures of alertness during the night shift and (2) decrease total sleep time during nocturnal sleep episodes on off-days. To accommodate the nested nature of the data (days nested within persons), analyses will be conducted in a multilevel modeling framework (19). Specifically, the total sleep time (TST), as an example, will be modeled as: $TST_{it} = \gamma_{00} + \gamma_{01} * group_i + u_{0i} + e_{it}$, where the TST obtained above for person i on day t , TST_{it} , are modeled separately as a function of between-person and within-person differences. Specifically, γ_{00} , indicates the expected TST score for a prototypical participant on a prototypical day (the reference category); γ_{01} captures between-group differences in sleep (placebo group vs. drug group); and u_{0i} and e_{it} capture additional between-person and occasion-specific differences not otherwise explained. All models will be fit using SAS 9.4 (proc mixed) with restricted maximum likelihood estimation. Effect size will be evaluated with respect to proportional reduction in unexplained variance from an informative baseline model (*pseudo-R²*, see (19)).

Exploratory measures:

While the primary measures in this study will examine *prospective* changes in sleep, we will also collect data that will

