examine *retrospective* changes in sleep. These include examining changes in subjective measures of sleep quality that are captured in the BSWSQ, ISI, and FOSQ-10 questionnaires. Changes on these questionnaires will be examined with repeated measure ANOVA. Another exploratory measure to be analyzed in the same manner will be a change in depressive symptom severity as captured on the CES-D. A final exploratory measure will be to examine the change in the number of caffeinated beverages during work shifts. Given that there is tremendous variability in the caffeine content of caffeinated beverages, within subject changes will be examined with multilevel modeling.

Power/Sample Size:

For estimation of sample size, we have reduced our aim to the single, most important outcome measure - will sleep efficiency improve in the drug condition - and reduced the statistical testing to a *t*-test. In previously published work (20), a variance of 3.62% - 3.87% was observed following use of 10 mg of suvorexant or placebo. For purposes of this sample size estimation, we can estimate $\sigma = 5.55\%$ (average variance * 150%, with the increase due to our use of actigraphy instead of polysomnography as a reporter). Setting $\alpha = 0.05$ and power = 80%, we would be able to detect a difference of 5.2% in sleep efficiency (i.e., that which was observed in a previous trial of 10 mg suvorexant in those with insomnia (21)) with 19 participants in each group (n=38 total).

**PROTOCOL
 APPLICATION FORM
 Human Subjects Research
 Stanford University**

Title : A double-blind, placebo-controlled, randomized, parallel design study to examine the effectiveness of 10 mg suvorexant in improving daytime sleep in shift workers

Approval Period: Draft

Protocol Director				
Name [name]		Degree (Program/year if student) PhD		Position, e.g. Assistant Professor, Resident, etc. Asst Professor
Department Psych/Sleep Medicine	Mail Code 5550	Phone [REDACTED]	Fax	E-mail [contact]
CITI Training current				Y

Admin Contact				
Name [name]		Degree (Program/year if student) BS		Position, e.g. Assistant Professor, Resident, etc.
Department Psychiatry and Behavioral Sciences	Mail Code 5550	Phone [REDACTED]	Fax	E-mail [contact]
CITI Training current				Y

Investigator				
Name		Degree (Program/year if student)		Position, e.g. Assistant Professor, Resident, etc.
Department	Mail Code	Phone	Fax	E-mail
CITI Training current				

Other Contact				

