After conclusion of the study, participants would be able to contact their physicians to obtain a prescription for the medication used in this study.

- g) Study Endpoint. What are the guidelines or end points by which you can evaluate the different treatments (i.e. study drug, device, procedure) during the study? If one proves to be clearly more effective than another (or others) during the course of a study, will the study be terminated before the projected total participant population has been enrolled? When will the study end if no important differences are detected?**

The primary endpoint of this study is a change in total sleep time during day time sleep episodes. Given the blinding of the study and the relatively small population being studied, we do not intend to examine the primary outcome prior to study completion (38 total subjects).

3. Background

- a) Describe past experimental and/or clinical findings leading to the formulation of the study.**

The hypocretins (orexins) are a pair of neuropeptides produced by a small group of hypothalamic neurons

Title : A double-blind, placebo-controlled, randomized, parallel design study to examine the effectiveness of 10 mg suvorexant in improving daytime sleep in shift workers
Approval Period: Draft

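### Section 2(g) makes change in daytime total sleep time the primary endpoint, but Section 2.7 ranks sleep efficiency first and computes power only for it, so power for the declared primary endpoint is not established

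*Combined protocol and SAP*

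**What the plan says.** Section 2(g), Study Endpoint, is the only place that uses the term primary endpoint: "The primary endpoint of this study is a change in total sleep time during day time sleep episodes". It adds that this outcome will not be examined before all 38 participants have finished.

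Section 2.7, Statistical Methods, has a main hypothesis that suvorexant "will significantly improve both objective (total sleep time, sleep efficiency, wake after sleep onset) and subjective (sleep quality) measures of sleep". The four measures are not ranked. A lower tier follows ("A secondary goal is to test the hypothesis that ingestion of 10 mg of suvorexant", on alertness during the shift and on nocturnal sleep on days off), and then exploratory questionnaire and caffeine measures. Total sleep time enters the analysis model as an illustration: "the total sleep time (TST), as an example, will be modeled as". The model has a group term, a person effect and a residual.

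Section 2.7, Power/Sample Size, states: "we have reduced our aim to the single, most important outcome measure - will sleep efficiency improve in the drug condition". For 19 per group at 5% alpha and 80% power it concludes: "we would be able to detect a difference of 5.2% in sleep efficiency". The SD of 5.55 points is built from published work in which "a variance of 3.62% - 3.87% was observed following use of 10 mg of suvorexant or placebo", and is described as "average variance * 150%, with the increase due to our use of actigraphy instead of polysomnography as a reporter".

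**The concern.** A trial of this size needs one outcome that decides whether it succeeded. Here a reader of 2(g) would look to total sleep time and a reader of the power paragraph to sleep efficiency. The tiers in 2.7 do not settle the matter, because both outcomes sit in the same unranked main hypothesis. If the two results disagree, either could be presented as the planned one.

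The sample-size justification also does not attach to the declared primary endpoint. The two outcomes are related, since sleep efficiency is total sleep time divided by time in bed, but power for one does not carry over to the other. Total sleep time also varies with time in bed, which the protocol does not fix; it only excludes people with less than 7 hours of opportunity for daytime sleep.

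Finally, 2(g) speaks of a change, while the model in 2.7 has no baseline or period term. The quantity to be estimated for the declared primary endpoint is therefore not fully defined either.

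**Working it through.** **1. The plan's own figure (sleep efficiency).** Inputs from Section 2.7: difference 5.2 points, SD 5.55, 19 per group, alpha 0.05, t-test. Sidedness is not stated; a two-sided test reproduces the plan's 19, whereas a one-sided test would need 15.

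- Standardised difference: 5.2 / 5.55 = 0.937
- Noncentrality: 0.937 × √(19/2) = 2.888, with 36 degrees of freedom and critical t = 2.028
- Power from the noncentral t distribution: **80.2%**. The figure reproduces.

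**2. The SD behind it.** The quantity is labelled a variance but used as an SD, and it is taken as an SD here.

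- Mean of the two quoted values: (3.62 + 3.87) / 2 = 3.745
- Times 1.5: 5.6175, or 5.62. The stated 5.55 equals 1.5 × 3.70.
- At 5.6175, power is 79.3% with 19 per group and 81.4% with 20.

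This is a small discrepancy and does not drive the finding.

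**3. What 19 per group can detect on total sleep time.** The documents give no difference and no SD, so only a standardised result follows from the plan. The same two-sided t-test reaches 80% power at a difference of **0.934 SD** of the analysed value. The SDs and gains below are assumptions used to show the range.

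| Assumed SD (min) | Detectable at 80% power (min) | Power for a 30 min gain | Power for a 45 min gain |
|---|---|---|---|
| 30 | 0.934 × 30 = 28.0 | 85% | 99% |
| 45 | 0.934 × 45 = 42.0 | 52% | 85% |
| 60 | 0.934 × 60 = 56.0 | 32% | 61% |

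**4. Does the 80% carry over?** Assume 420 minutes in bed, matching the 7-hour minimum opportunity. The 5.2-point gain becomes 0.052 × 420 = 21.8 min, and the SD of 5.55 points becomes 0.0555 × 420 = 23.3 min. Power is then again 80.2%, but only if time in bed does not vary. If the SD of total sleep time were 30 min, power for 21.8 min would be 59%; at 45 min it would be 31%; at 60 min, 19%.

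**5. Effect of using baseline.** With baseline as a covariate at correlation r, the detectable difference is approximately 0.934 × √(1 − r²). At assumed r = 0.5 this is 0.81 SD, and at r = 0.7 it is 0.67 SD. The reading given to change in 2(g) therefore affects power materially.

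**The case against.** The best defence is that there is no real conflict. Only 2(g) uses the term primary endpoint, and it is unambiguous. The sleep-efficiency sentence concerns sample-size estimation, and the same sentence also simplifies the multilevel model to a t-test, so it can be read as a planning device. This softens the conflict but does not remove it: the paragraph justifies its choice by importance rather than convenience, and sizing on a non-primary outcome still leaves the primary one without a power statement.

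Other objections are partly right:

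- The 5.55 may rest on more than two values in the cited work, in which case 5.62 is not proven correct. The documents cannot settle this, so the figure needs explaining or correcting, and the effect on power is under one percentage point.
- Section 2.7 does say that data from both the baseline and the intervention weeks will be used in the analyses. The gap is that the model does not show how.
- The minute-scale results depend on assumed SDs and gains. Only 0.934 SD follows from the plan's sample size, alpha and power, with two-sided testing inferred. The minute figures show how wide the uncertainty is; they are not evidence of low power.

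**Conclusion.** The concern holds and should be resolved before unblinding. Sections 2(g) and 2.7 put different outcomes first, nothing else in the documents reconciles them, and the 80% power belongs to sleep efficiency only. For total sleep time the supportable statement is that 19 per group detects 0.93 SD with 80% power (two-sided 5% t-test, no baseline adjustment). Across the tabulated SDs of 30 to 60 min and gains of 30 or 45 min, power runs from 32% to 99%, so the trial may be adequately powered or not. The seriousness rests on the unresolved choice of primary endpoint; the SD arithmetic and the missing baseline term are secondary points.

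**What to change.** Before unblinding, name the same single primary endpoint in 2(g) and 2.7. Which one is the sponsor's choice. Label the remaining main-hypothesis sleep measures secondary, alongside the secondary goals already listed.

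- **If total sleep time is primary:** replace the 80% statement with the power or detectable difference for total sleep time, from a stated difference and SD. Say whether and how baseline enters the model, so that the change named in 2(g) matches the analysis.
- **If sleep efficiency is primary:** amend 2(g) and keep the sample-size statement, with the SD of 5.55 either explained or corrected to 5.62.

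The cost is a wording change in two sections and one restated or confirmed power figure. Data collection and the 38 participants are unaffected. The downside is that results on the other sleep measures will count only as secondary evidence, and a restated power for total sleep time may be less favourable than 80%.

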5.1 Device Name : Actiwatch2

Describe the device to be used.

Gross motor activity monitor (similar to a FitBit)

Manufacturer Resironics

IDE Exemption

Y This is a legally marketed device being used in accordance with its labeling.

5.2 Device Name : ApneaLink

Describe the device to be used.

This device monitors breathing (nasal cannula) and blood oxygenation and heart rate (finger pulse oximetry)

Manufacturer Resmed

IDE Exemption

Y This is a legally marketed device being used in accordance with its labeling.

Title : A double-blind, placebo-controlled, randomized, parallel design study to examine the effectiveness of 10 mg suvorexant in improving daytime sleep in shift workers

Approval Period: Draft

6. Drugs, Reagents, or Chemicals

- a) Please list in the table below all investigational drugs, reagents or chemicals to be administered to participants.
- b) Please list in the table below all commercial drugs, reagents or chemicals to be administered to participants.

6.1 Drug Name : Suvorexant

Source (i.e. Pharmacy, Sponsor, Merck Pharmaceuticals etc.) :

If not pre-mixed, where will the material be mixed and by whom:

Manufacturer : Merck Pharmaceuticals

IND# (if available) :

Dosage : 10 or 20 mg

Administration Route:

IND Exemption

- N** Is this new and different uses of this commercially available drug, reagent or chemical?
- Y** Are all of these IND Statements true?

Investigational New Drug (IND) Regulations

The IND Regulations [21 CFR 312.2(b)] state that clinical investigation of a drug product is exempt from the requirements for an IND if all of the following apply:

- The Drug used in the investigations is lawfully marketed in the United States.
- The investigation is not intended to be reported to FDA in support of new indication for use or to support any other significant change in the labeling for the drug.
- The investigation is not intended to support a significant change in the advertising of the product.
- The investigation does not involve a route of administration or dosage level, use in a participant population, or other factor that significantly increases the risks (or decreases the acceptability of the risks) associated with the use of the drug product.
- The investigation is conducted in compliance with the requirements for IRB review and informed consent [21 CFR parts 56 and 50].
- The investigation is conducted in compliance with the requirements concerning the promotion and sale of drugs [21 CFR part 312.7], e.g., the drug may not be represented as safe or effective for the purposes for which it is under investigation, nor may it be commercially distributed or sold.

7. Medical Equipment for Human Subjects and Laboratory Animals

Title : A double-blind, placebo-controlled, randomized, parallel design study to examine the effectiveness of 10 mg suvorexant in improving daytime sleep in shift workers

Approval Period: Draft

If medical equipment used for human patients/participants is also used on animals, describe such equipment and disinfection procedures.

n/a

8. Participant Population

- a) **State the following: (i) the number of participants expected to be enrolled at Stanford-affiliated site(s); (ii) the total number of participants expected to enroll at all sites; (iii) the type of participants (i.e. students, patients with certain cancer, patients with certain cardiac condition) and the reasons for using such participants.**

(i) We anticipate that we will enroll 38 participants to completion. We estimate that this will require 50 participants beginning the study (i.e., at least signing a consent form).
 (ii) This is a single-site investigation
 (iii) This study will examine healthy individuals who work at night and have difficulty initiating or maintaining sleep during the day. We are specifically studying the effectiveness of this medication on this condition.

- b) **State the age range, gender, and ethnic background of the participant population being recruited.**

Age: 20-60 years
 Gender: all
 Ethnicity: all with recruitment targeting the ethnicity distribution of individuals involved in night work in the catchment area

- c) **State the number and rationale for involvement of potentially vulnerable subjects in the study (including children, pregnant women, economically and educationally disadvantaged, decisionally impaired, homeless people, employees and students). Specify the measures being taken to minimize the risks and the chance of harm to the potentially vulnerable subjects and the additional safeguards that have been included in the protocol to protect their rights and welfare.**

Vulnerable subjects will not be specifically recruited.

- d) **If women, minorities, or children are not included, a clear compelling rationale must be provided (e.g., disease does not occur in children, drug or device would interfere with normal growth and development, etc.).**

Children are not included as they do not typically work night shifts and the effect of this drug on their developing brain is unknown.

- e) **State the number, if any, of participants who are laboratory personnel, employees, and/or students. They should render the same written informed consent. If payment is allowed, they should also receive it. Please see Stanford University policy.**

We are not specifically targeting laboratory personnel, employees, or students, though they are not explicitly excluded. Should they be recruited, they will sign the same consent as all subjects and receive payment as allowed.

- f) **State the number, if any, of participants who are healthy volunteers. Provide rationale for the inclusion of healthy volunteers in this study. Specify any risks to which participants may possibly be exposed. Specify the measures being taken to minimize the risks and the chance of harm to the volunteers and the additional safeguards that have been included in the protocol to protect their rights and welfare.**

All participants will be healthy volunteers. The main risk to which they are exposed, over the risks they normally encounter in their lives, is taking a prescription medication. There is a favorable side-effect profile with minimal risk reported in taking this medication. The medication being prescribed is being used to specifically treat a sleep disorder in these volunteers.

- g) **How will you identify and recruit potential participants about the research study? (E.g., by: chart**

Title : A double-blind, placebo-controlled, randomized, parallel design study to examine the effectiveness of 10 mg suvorexant in improving daytime sleep in shift workers

Approval Period: Draft

review; notified by treating physician; response to ad). All final or revised recruitment materials, flyers, etc. must be submitted to the IRB for review and approval before use. You may not contact potential participants prior to IRB approval. See Advertisements: Appropriate Language for Recruitment Material.

Participants will be recruited by flyers and online advertising.

h) Inclusion and Exclusion Criteria.

Identify inclusion criteria.

- Aged 20-60 (older individuals excluded due to altered sleep-related circadian signaling)
- Males and females
- Shift worker
 - # Minimum of three months of prior shift work
 - # Will work minimum of four nights per week or 32 hours of night shift per week during study
 - # "Night work" defined as having at least six hours of work occurring between 8 PM and 8 AM and no longer than 12 hours on shift
- Presence of DSM-5 defined Circadian Rhythm Sleep-Wake Disorder: Shift Work Type
 - # Insomnia (SE < 88%) during attempted daytime sleep or excessive sleepiness during nocturnal wake

Identify exclusion criteria.

- Currently or planning to become pregnant
- Currently breastfeeding
- Inadequate opportunity (<7 hours) for daytime sleep after shift work
- Use of sleep aids during the study period. Includes as needed or continuous use of prescription, non-prescription, and naturopathic pharmacotherapies
- Diagnosis or detection (during study) of sleep disordered breathing (AHI>10) on home sleep testing; referral to clinical sleep program will be offered
- Diagnosis of narcolepsy
- Restless Legs Syndrome
- >600 mg caffeine intake per night shift or use of prescription stimulant medication during night shift
- Rotational or irregular work shifts during study
- Use of digoxin for six months prior to or during study
- Use of strong (e.g., etoconazole, itraconazole, posaconazole, clarithromycin, nefazodone, ritonavir, saquinavir, nelfinavir, indinavir, boceprevir, telaprevir, telithromycin, conivaptan) or moderate (e.g., amprenavir, aprepitant, atazanavir, ciprofloxacin, diltiazem, erythromycin, fluconazole, fosamprenavir, grapefruit juice, imatinib, verapamil) CYP3A inhibitors or CYP3A inducers (e.g., rifampin, carbamazepine, phenytoin) for six months prior to or during study
- Severe hepatic impairment
- Unstable or severe medical or psychiatric condition

i) Describe your screening procedures, including how qualifying laboratory values will be obtained. If you are collecting personal health information prior to enrollment (e.g., telephone screening), please request a waiver of authorization for recruitment (in section 15).

Screening procedures will be done in a private room at VAPAHCS. Laboratory values will be obtained after a nurse draws blood and collects urine from the participant at the VAPAHCS Clinical Studies Unit.

j) Describe how you will be cognizant of other protocols in which participants might be enrolled. Please explain if participants will be enrolled in more than one study.

We will ask subjects during the recruitment and screening process whether they are enrolled in any other study. Participants enrolled in other studies will not be enpaneled in this study.

k) Payment/reimbursement. Explain the amount and schedule of payment or reimbursement, if any, that will be paid for participation in the study. Substantiate that proposed payments are reasonable and commensurate with the expected contributions of participants and that they do not constitute undue pressure on participants to volunteer for the research study. Include provisions for prorating payment. See payment considerations

Title : A double-blind, placebo-controlled, randomized, parallel design study to examine the effectiveness of 10 mg suvorexant in improving daytime sleep in shift workers

Approval Period: Draft

Subjects will be paid [REDACTED] for completing all aspects of the protocol, not including screening. This will be broken down as: [REDACTED] per week of study (5 weeks = [REDACTED] + [REDACTED] completion incentive. This is payable after completion of the individual's study. Individuals who complete only part of the study will receive a prorated amount, not including the completion incentive.

l) Costs. Please explain any costs that will be charged to the participant.

Participants will not be charged for engaging in this study.

m) Estimate the probable duration of the entire study. Also estimate the total time per participant for: (i) screening of participant; (ii) active participation in study; (iii) analysis of participant data.

We estimate that that study will take two years to complete subject empanelment and analysis. Screening participants will take approximately three hours each. Participants will then be active in the protocol for five weeks. Analysis of data will take approximately 6 months.

9. Risks

- a) For the following categories include a scientific estimate of the frequency, severity, and reversibility of potential risks. Wherever possible, include statistical incidence of complications and the mortality rate of proposed procedures. Where there has been insufficient time to accumulate significant data on risk, a statement to this effect should be included. (In describing these risks in the consent form to the participant it is helpful to use comparisons which are meaningful to persons unfamiliar with medical terminology.)

The risks of the Investigational devices.

None

The risks of the Investigational drugs. Information about risks can often be found in the Investigator's brochure.

None

The risks of the Commercially available drugs, reagents or chemicals. Information about risks can often be found in the package insert.

There is a risk of an unknown side-effect from taking this FDA-approved medication. The most common side-effect is sleepiness. As such, we require that subjects only take the medication when they have at least 7 hours of time to sleep.

The risks of the Procedures to be performed. Include all investigational, non-investigational and non-invasive procedures (e.g., surgery, blood draws, treadmill tests).

There is the possibility of a small scar to form at the site of venipuncture. This risk is increased in individuals with darker skin pigmentation.

The risks of the Radioisotopes/radiation-producing machines (e.g., X-rays, CT scans, fluoroscopy) and associated risks.

None

The risks of the Physical well-being.

The wrist worn activity monitors may cause a rash (contact dermatitis) on the wrist underneath where the device makes contact with the skin. This risk is similar to wearing a wrist watch. If this occurs, we will recommend that participants move the watch and use skin cream on the rash.

The risks of the Psychological well-being.

There is a possibility of increased depressive symptoms following use of this medication. We will monitor this at the end of the first week of drug use. There is always a risk when completing questionnaires that participants will learn something about themselves that negatively affects their psychological well-being.

The risks of the Economic well-being.

Title : A double-blind, placebo-controlled, randomized, parallel design study to examine the effectiveness of 10 mg suvorexant in improving daytime sleep in shift workers

Approval Period: Draft

There is no likely risk to economic well-being.

The risks of the Social well-being.

There is no likely risk to social well-being.

Overall evaluation of Risk.

Low - innocuous procedures such as phlebotomy, urine or stool collection, no therapeutic agent, or safe therapeutic agent such as the use of an FDA approved drug or device.

- b) If you are conducting international research, describe the qualifications/preparations that enable you to both estimate and minimize risks to participants. Provide an explanation as to why the research must be completed at this location and complete the [LINKFORINTERNATIONALRESEARCHFORM] International Research Form. If not applicable, enter N/A.**

n/a

- c) Describe the planned procedures for protecting against and minimizing all potential risks. Include the means for monitoring to detect hazards to the participant (and/or to a potential fetus if applicable). Include steps to minimize risks to the confidentiality of identifiable information.**

Two weeks after initiating the baseline portion of the study, participants will return to the lab and be monitored for risk exposure. One week after initiating medication, subjects will again return to the lab and be monitored for risk exposure.

- d) Explain the point at which the experiment will terminate. If appropriate, include the standards for the termination of the participation of the individual participant Also discuss plans for ensuring necessary medical or professional intervention in the event of adverse effects to the participants.**

The experiment will terminate at the end of the three weeks of drug administration. In case of an adverse event during the protocol, Drs. [name] and [name] will be able to advise a proper course of action.

- e) Data Safety and Monitoring Plan (DSMP). See guidance on Data Safety and Monitoring.**

A Data and Safety Monitoring Plan (DSMP) is required for studies that present Medium or High risk to participants. (See Overall Evaluation of Risk above). If Low Risk, a DSMP may not be necessary. Multi-site Phase III clinical trials funded by NIH require the DSM Plan to have a Data Safety Monitoring Board or Committee (DSMC or DSMB). The FDA recommends that all multi-site clinical trials that involve interventions that have potential for greater than minimal risk to study participants also have a DSMB or DSMC.

The role of the DSMC or DSMB is to ensure the safety of participants by analyzing pooled data from all sites, and to oversee the validity and integrity of the data. Depending on the degree of risk and the complexity of the protocol, monitoring may be performed by an independent committee, a board (DSMC/DSMB), a sponsor's Data Safety Committee (DSC), a Medical Monitor, a sponsor's safety officer, or by the Protocol Director (PD).

Describe the following:

What type of data and/or events will be reviewed under the monitoring plan, e.g. adverse events, protocol deviations, aggregate data?

Adverse events, consent forms, and protocol deviations will be monitored.

Identify who will be responsible for Data and Safety Monitoring for this study, e.g. Stanford Cancer Institute DSMC, an independent monitoring committee, the sponsor, Stanford investigators independent of the study, the PD, or other person(s).

The PD in collaboration with Drs. [name] and [name] will be the responsible entity.

Provide the scope and composition of the monitoring board, committee, or safety monitor, e.g., information about each member's relevant experience or area of expertise. If the Monitor is the

Title : A double-blind, placebo-controlled, randomized, parallel design study to examine the effectiveness of 10 mg suvorexant in improving daytime sleep in shift workers

Approval Period: Draft

Stanford Cancer Center DSMC or the PD, enter N/A.

In addition to the PD, Drs. [name] and [name] will consult on all medically-related issues. Both are board-certified sleep clinicians.

Confirm that you will report Serious Adverse Events (SAEs), Suspected Unexpected Serious Adverse Reactions (SUSARs), or Unanticipated Problems (UPs) to the person or committee monitoring the study in accordance with Sponsor requirements and FDA regulations.

SAE, SUSAR, and UP will each be reported to the IRB and Merck (sponsor) in accordance with the Sponsor's requirements and FDA regulations.

If applicable, how frequently will the Monitoring Committee meet? Will the Monitoring Committee provide written recommendations about continuing the study to the Sponsor and IRB?

[name] will monitor all data continuously and will meet with the other members of the Monitoring Committee as needed.

Specify triggers or stopping rules that will dictate when the study will end, or when some action is required. If you specified this in Section 2g [Study Endpoints], earlier in this application enter 'See 2g'.

Any SAE or SUSAR will result in the immediate termination of the study.

Indicate to whom the data and safety monitoring person, board, or committee will disseminate the outcome of the review(s), e.g., to the IRB, the study sponsor, the investigator, or other officials, as appropriate.

The PD will disseminate the outcomes of all discussion to the IRB, study sponsor, and FDA, as appropriate.

Select One:

- The Protocol Director will be the only monitoring entity for this study.
- Y This protocol will utilize a board, committee, or safety monitor as identified in question #2 above.

10. Benefits

- a) **Describe the potential benefit(s) to be gained by the participants or by the acquisition of important knowledge which may benefit future participants, etc.**

Participants may find the medication helpful for treating their shift work sleep disorder and would be able to speak with their primary care physician about the appropriateness of a prescription. This study would increase our knowledge about how to appropriately treat shift work sleep disorders.

11. Privacy and Confidentiality

Privacy Protections

- a) **Describe how the conditions under which interactions will occur are adequate to protect the privacy interests of participants (e.g., privacy of physical setting for interviews or data collection, protections for follow-up interactions such as telephone, email and mail communications).**

Direct interactions will occur in a private room at VAPAHCS as well as at the Clinical Studies Unit at VAPAHCS. We will primarily use the telephone to communicate issues of scheduling with the participants.

Confidentiality Protections

Title : A double-blind, placebo-controlled, randomized, parallel design study to examine the effectiveness of 10 mg suvorexant in improving daytime sleep in shift workers

Approval Period: Draft

- b) Specify PHI (Protected Health Information). PHI is health information linked to HIPAA identifiers (see above). List BOTH health information AND HIPAA identifiers. If you are using STARR, use the Data Privacy Attestation to ensure that your request will match your IRB-approved protocol. Be consistent with information entered in section 15a.**

We will obtain the following PHI:

Name

Social Security number

Telephone number

Local address

Birth date

Electronic mail addresses

- c) You are required to comply with University Policy that states that ALL electronic devices: computers (laptops and desktops; OFFICE or HOME); smart phones; tablets; external hard disks, USB drives, etc. that may hold identifiable participant data will be password protected, backed up, and encrypted. See <http://med.stanford.edu/datasecurity/> for more information on the Data Security Policy and links to encrypt your devices.**

Provide any additional information on ALL data security measures you are taking. You must use secure databases such as <https://researchcompliance.stanford.edu/panels/hs/redcap> RedCap. If you are unsure of the security of the system, check with your Department IT representative. Please see <http://med.stanford.edu/irt/security/> for more information on IRT Information Security Services and http://www.stanford.edu/group/security/securecomputing/mobile_devices.html for more information for securing mobile computing devices. Additionally, any PHI data on paper must be secured in an locked environment.

By checking this box, You affirm the aforementioned. Y

PHI will be stored on paper in a locked cabinet in a locked room in a locked wing of Building 4 at VAPAHCS. Deidentified data will be stored on encrypted Stanford desktop computers backed up with Crash Plan Pro.

- d) Describe how data or specimens will be labeled (e.g. name, medical record number, study number, linked coding system) or de-identified. If you are de-identifying data or specimens, who will be responsible for the de-identification? If x-rays or other digital images are used, explain how and by whom the images will be de-identified.**

All data are de-identified. The subject coordinator assigns a sequential random code (e.g., SUV001) each participant once the participant signs a consent form.

- e) Indicate who will have access to the data or specimens (e.g., research team, sponsors, consultants) and describe levels of access control (e.g., restricted access for certain persons or groups, access to linked data or specimens).**

All members of the research team will have access to all data.

- f) If data or specimens will be coded, describe the method in which they will be coded so that study participants' identities cannot be readily ascertained from the code.**

Our lab assigns a random code with the first part indicating the study in which the individual is participating and the second the sequential number of the participant.

- g) If data or specimens will be coded, indicate who will maintain the key to the code and describe how it will be protected against unauthorized access.**

The key to the code is kept on paper in a locked file cabinet in a locked room in a locked wing of Building 4 at VAPAHCS. All team members have access to this information.

- h) If you will be sharing data with others, describe how data will be transferred (e.g., courier, mail) or transmitted (e.g., file transfer software, file sharing, email). If transmitted via electronic networks, describe how you will secure the data while in transit. See <http://www.stanford.edu/group/security/securecomputing/>**

Title : A double-blind, placebo-controlled, randomized, parallel design study to examine the effectiveness of 10 mg suvorexant in improving daytime sleep in shift workers

Approval Period: Draft

<http://www.stanford.edu/group/security/securecomputing/>. Additionally, if you will be using or sharing PHI see <https://uit.stanford.edu/security/hipaa> <https://uit.stanford.edu/security/hipaa>.

n/a

